1.2.4 Clinical Safety

For nivolumab monotherapy, the safety profile is similar across tumor types (investigator brochure v 2015). The only exception is pulmonary inflammation adverse events (AEs), which may be numerically greater in subjects with NSCLC, because in some cases, it can be difficult to distinguish between nivolumab-related and unrelated causes of pulmonary symptoms and radiographic changes. There is no pattern in the incidence, severity, or causality of AEs to nivolumab dose level. Safety data for subjects with previously treated advanced or metastatic NSCLC treated with nivolumab monotherapy in CA209017 (131 subjects), CA209057 (287 subjects), and CA209063 (117 subjects) were pooled and safety analyses were performed for these pooled subjects who receiving nivolumab monotherapy (a total of 535 subjects)(investigator brochure v 2015). Based on the pooled analyses, nivolumab monotherapy at a dose of 3 mg/kg administered IV Q2W has an acceptable safety profile, as demonstrated by the frequency, severity, and types of AEs, drug-related deaths, SAEs, and AEs leading to discontinuation. The most common adverse events were fatigue (19.6%), decreased appetite (12.3%), nausea (12.0%), and asthenia (10.5%). The majority of drug-related AEs were of Grade 1-2 in severity.

The toxicity profile of ipilimumab at the dose of 3mg/Kg for 4 doses in previously treated patients with metastatic melanoma was assessed in phase 3 trial. One hundred and thirty one patients with received ipilimumab as monotherapy, 380 received it with gp100 peptide, and 132 received gp100 peptide vaccine alone. Patients in the study received a median of 4 doses. Ipilimumab was discontinued for adverse events in 10% of patients. The most common adverse events in patients who received ipilimumab at 3mg/Kg were fatigue (31%), pruritus (23%) and rash (22%)(package insert v 2013). The majority of drug-related AEs were of Grade 1-2 in severity.

In several ongoing clinical trials, the safety of nivolumab in combination with ipilimumab is being explored. Most studies are ongoing and, as such, the safety profile of nivolumab combinations continues to evolve. The most advanced combination under development is nivolumab + ipilimumab in subjects with melanoma. Thus far, the combination of both agents results in a safety profile with similar types of AEs as either agent alone, but in some cases with a greater frequency ³³.

Safety data for subjects with previously untreated unresectable or metastatic melanoma treated with nivolumab in combination with ipilimumab in phase III (313 subjects) and phase II (94subjects) trials were pooled and safety analyses were performed for these pooled subjects receiving nivolumab in combination with ipilimumab (a total of 407 subjects) as described in the investigator brochure BMS-936558/MDX1106 Version No14, 30-Jun-2015.^{32,39} Based on the pooled analyses, nivolumab 1 mg/kg combined with ipilimumab 3 mg/kg administered IV Q3W for 4 doses followed by nivolumab 3 mg/kg IV Q2W has an acceptable safety profile, as demonstrated by the frequency, severity, and types of AEs, drug-related deaths, SAEs, and AEs leading to discontinuation. The most frequently reported drug-related AEs of any grade were diarrhea (43.0%), fatigue (35.4%), pruritus (33.4%), rash (31.0%), nausea (24.8%), pyrexia (18.7%), ALT increased (18.2%), AST increased (16.7%) and decreased appetite (16.2%). The most frequently reported drug-related Grade 3-4 AEs ($\geq 5\%$ of subjects) were colitis (9.6%), diarrhea (8.80%), ALT increased (8.4%), lipase increased (8.4%), and AST increased (5.9%). Study drug toxicity was considered responsible for 2 deaths; 1 subject died of ventricular arrhythmia within 30 days of the last dose and the other died of pneumonitis between 31 and 100 days of the last dose.

NU Study Number: NU 16B07
Other Study Number: CA 209-782

Most recently, nivolumab at 3mg/Kg every 2 weeks combined with ipilimumab at 1mg/Kg every 6 weeks was administered in patients with advanced NSCLC in the first line setting.(CheckMate 012 trial)⁴³ In this trial 4 different combinations of nivolumab were compared (nivolumab 1mg/Kg every 3 weeks x 4+ ipilimumab 1mg/Kg every 3 weeks x 4 followed nivolumab 3mg/Kg every 2 weeks (N=31), nivolumab 1mg/Kg every 2 weeks + ipilimumab 1mg/kg every 6 weeks (N=40), nivolumab 3mg/Kg every 2 weeks + ipilimumab 1mg/Kg every 12 weeks (n=38) and finally nivolumab 3mg/Kg every 2 weeks combined with ipilimumab 1mg/Kg every 6 weeks until disease progression (n=46). Toxicity data favored the latter group with estimates of grade 3 and 4 treatment related adverse events 29, 35, 29 and 28%, respectively. These results indicate that the nivolumab dose of 3mg/Kg administered every 2 weeks combined with ipilimumab 1mg/Kg every 6 weeks until disease progression has favorable disease profile and should be further explored in future clinical trials.

1.2.5 Biomarkers

Significant efforts continue to explore potential tumor cells and microenvironment-related biomarkers that could predict response to nivolumab and other checkpoint inhibitors. For instance, tumor cell expression of PD-L1 was characterized with the use of IHC staining and pharmacodynamics changes in the peripheral blood absolute lymphocyte count in the study investigating the combination of nivolumab and ipilimumab in melanoma ³³. PD-L1 positivity was defined as expression in at least 5% of tumor cells. Among patients treated with the concurrent regimen of nivolumab and ipilimumab, ORs were observed in patients with either PD-L1-positive tumor samples (6 of 13 patients) or PD-L1-negative tumor samples (9 of 22). In the sequenced regimen cohorts, a higher number of overall responses were seen among patients with PD-L1-positive tumor samples (4 of 8 patients) than among patients with PD-L1-negative tumor samples (1 of 13) suggesting the possibility that these tumors have higher response rates to the combination. Other biomarkers such as tissue expression of PDL-2, interferon- γ (IFN- γ), IDO (indoleamine-pyrrole 2,3-dioxygenase), and T cell CD8+ infiltration are also being investigated. However, there is no definitive date to support the use of any of these biomarkers to select patients for treatment at this time.

1.3 Rationale for the Current Study

IBC is associated with significant level of genomic instability. Moreover, the level of genomic mutation rate, indicated as iScore is associated with infiltrate of CD8 cytotoxic T cells together with PDL-1 staining. Immune checkpoint targeted therapies showed significant activity and is currently approved in other solid tumors. The data provide a strong rationale for testing of immune checkpoint modulators in metastatic IBC.

1.3.1 Study design

The rationale for use of a “window of opportunity” study is based on the fact that it allows to assess the efficacy of immunotherapy in IBC when the tumor is still unperturbed by other systemic treatments routinely used the metastatic setting.

1.3.2 Nivolumab flat dose regimen

The safety and efficacy of 240 mg (combined with 1mg/kg of ipilimumab) Q2W flat dose of nivolumab is expected to be similar to the 3 mg/kg Q2W dosing regimen. Using the PPK model, exposure of nivolumab at 240 mg flat dose is identical to a dose of 3 mg/kg for subjects weighing 80 kg, which is the approximate median body weight in nivolumab clinical trials. Across the various tumor types in the clinical program, nivolumab has been shown to be safe and well tolerated up to a dose level of 10 mg/kg, and the relationship between

NU Study Number: NU 16B07
Other Study Number: CA 209-782

nivolumab exposure produced by 3 mg/kg and efficacy and safety has been found to be relatively flat. Given the similarity of nivolumab PK across tumor types and the similar exposures predicted following administration of 240 mg flat dose compared to 3 mg/kg, it is expected that the safety and efficacy profile of 240 mg nivolumab will be similar to that of 3 mg/kg nivolumab. Hence, the flat dose of 240 mg nivolumab is under investigation.

1.3.3 IpiLimumab dose regimen

IpiLimumab will be administered at 1mg/Kg every 6 weeks until disease progression in combination with nivolumab 240mg every 2 weeks. As discussed above, this drug combination regimen has been compared with the current FDA approved combination regimen of nivolumab 1mg/Kg every 3 weeks x 4 and ipiLimumab 3mg/Kg every 3 weeks x 4 followed by nivolumab 3mg/Kg every 2 weeks until disease progression and showed favorable toxicity profile with maintained efficacy among patient with lung cancer.⁴³

1.4 Exploratory Studies

In the era of personalized therapy appropriate patient selection to immune-check point inhibitors remain an elusive goal. There are conflicting data on the predictive value of PD-L1 expression on PD-1 directed therapy in solid tumors^{30,44}. Herbst et al showed that patients with solid tumors including non-small cell lung cancer and melanoma treated with humanized PD-L1 antibody had higher ORR when immunohistochemistry showed intense staining for PD-L1 in the tumor⁴⁵. The same correlation was not observed on stratified analysis according to tumor cell membrane PD-L1 expression of non-small cell lung cancer patients treated with nivolumab therapy in the second line setting.³⁰

The most recent archival diagnostic tissue biopsy performed as part of the standard of care approach to recurring breast cancer will be obtained for all patients and sent for NGS and evaluation of iScore (baseline assessment). The same specimen will be assessed for PDL-1 expression. A fresh tissue biopsy will be obtained for all patients where archival tissue is not available.

Should repeat tumor tissue biopsy be performed after initiation of treatment on protocol as part of standard of care approach, specimens will be sent for NGS, iScore and PDL-1 staining. Correlations between efficacy endpoints (PFS and ORR) and biomarker statuses will be conducted.

2.0 OBJECTIVES & ENDPOINTS

2.1 Primary Objective & Endpoint

To determine progression free survival (PFS) in patients with newly recurrent HER2 negative IBC treated with nivolumab and ipilimumab according to Response Evaluation Criteria in Solid Tumors (RECIST) v 1.1.⁴⁶

The time in months from start of treatment to progression or death will be measured for all patients who receive at least one dose of study drug. Patients will be followed up to 2 years after completion of treatment.

2.2 Secondary Objectives & Endpoints

2.2.1 To assess the overall response rate (ORR) and clinical benefit rate (CBR) according to RECIST criteria v1.1, in patients with recurrent IBC treated with nivolumab and ipilimumab

Overall response rate (ORR) is defined as Complete Response (CR) + Partial Response (PR). Clinical benefit rate (CBR) is defined as CR + PR + Stable Disease (SD). Patients will have scans every 12 weeks.

2.2.2 To assess overall survival in patients with recurrent HER2 negative IBC treated with nivolumab and ipilimumab.

Patients will be followed from the start of treatment until 2 years post-treatment or death, whichever occurs first, and average survival time will be measured.

2.2.3 To assess the safety and tolerability of nivolumab and ipilimumab in patients with recurrent IBC according to the National Cancer Institute Common Terminology Criteria Adverse events v 4.03).

The number, frequency, and severity of adverse events will be collected from time of consent until 12 weeks after study treatment.

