6.3 Secondary Endpoints

- Overall response rate (ORR, defined as Complete Response (CR) + Partial Response (PR)), and Clinical Benefit Rate (CBR, defined as CR + PR + Stable Disease (SD)) in patients with newly recurrent IBC treated with nivolumab and ipilimumab
- Overall survival defined as time in months from the date of first study treatment to the date of death.
- The number, frequency, and severity of adverse events will be collected from the time of consent until 12 weeks after study treatment to evaluate safety of nivolumab and ipilimumab in patients with IBC. Adverse events will follow National Cancer Institute Common Terminology Criteria for Adverse Events (CTCAE) version 4.03

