6.6 Response Criteria

6.6.1 Evaluation of target lesions

Complete Response (CR): Disappearance of all target lesions. Any pathological lymph nodes (whether target or non-target) must have reduction in short axis to <10mm.

Partial Response (PR): At least a 30% decrease in the sum of the diameters of target lesions, taking as reference the baseline sum diameters.

Progressive Disease (PD): At least a 20% increase in the sum of the diameters of target lesions, taking as reference the smallest sum on study (this includes the baseline sum if that is the smallest on study). In addition to the relative increase of 20%, the sum must also demonstrate an absolute increase of at least 5 mm (0.5 cm). (Note: the appearance of one or more new lesions is also considered progressions).

Stable Disease (SD): Neither sufficient shrinkage to qualify for PR nor sufficient increase to qualify for PD, taking as reference the smallest sum diameters while on study.

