6.6.2 Evaluation of Non-Target Lesion

Complete Response (CR): Disappearance of all non-target lesions and normalization of tumor marker level. All lymph nodes must be non-pathological in size (<10 mm [<1 cm] short axis).

Non-CR/Non-PD: Persistence of one or more non-target lesion(s) and/or maintenance of tumor marker level above the normal limits.

Progressive Disease (PD): Appearance of one or more new lesions and/or unequivocal progression of existing non-target lesions. Unequivocal progression should not normally trump target lesion status. It must be representative of overall disease status change, not a single lesion increase.

Although a clear progression of "non-target" lesions only is exceptional, the opinion of the treating physician should prevail in such circumstances, and the progression status should be confirmed at a later time by the review panel (or Principal Investigator).

NU Study Number: NU 16B07
Other Study Number: CA 209-782

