6.6.4 Duration of response

Duration of overall response: The duration of overall response is measured from the time measurement criteria are met for CR or PR (whichever is first recorded) until the first date that recurrent or progressive disease is objectively documented (taking as reference for progressive disease the smallest measurements recorded since the treatment started).

The duration of overall CR is measured from the time measurement criteria are first met for CR until the first date that progressive disease is objectively documented.

Duration of stable disease: Stable disease is measured from the start of the treatment until the criteria for progression are met, taking as reference the smallest measurements recorded since the treatment started, including the baseline measurements.

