10.2 Sample Size and Accrual

We previously identified 44 patients who were included in a retrospective study of the prognostic significance of HER2 status in IBC. These patients had both HER2 negative and HER2 positive disease, developed metastases, and experienced a disease progression. The median time from the first progression of their metastatic disease to the second progression event or death was approximately 3 months. These patients will be considered our historical control group.

Nivolumab ipilimumab combination will be considered of interest for further study if the median PFS time is increased to at least 6 months. We will test the null hypothesis that median PFS is at most 3 months versus the alternative that it is at least 6 months. The null corresponds to 25% PFS at 6 months under the exponential distribution of PFS versus an alternative 6 month PFS rate of 50%. The null corresponds to 50% PFS at 3 months and the alternative corresponds to 70.71% PFS at 3 months under the same conditions.

We will initially recruit and treat 15 patients. If 7 or fewer initial cohort patients are progression free at 3 months the study will be terminated for lack of efficacy. If at least 8/15 are progression-free at 3 months then we will recruit an additional 14 patients for a total of 29.

The patients free of progression at 3 months from the initial cohort will remain on study until either progression or 6 months evaluation. Second cohort patients will be evaluated at 6 months only. If at least 11/29 patients are progression free at 6 months the null hypothesis will be rejected.

The chance of early study termination (3 months follow up with 15 patients) is 50% under the null and 4.4% under the alternative. Study power is 90% with overall type I error of 7%. The design follows: Early stopping designs based on progression-free survival at an early time point in the initial cohort.⁴⁹

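### The clinical benefit rate sets no minimum duration for stable disease, has no rule for Non-CR/Non-PD and has two conflicting denominators, so its value turns on an unwritten coding choice

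*Combined protocol and SAP*

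**What the plan says.** Section 2.2.1 gives the formula: "Clinical benefit rate (CBR) is defined as CR + PR + Stable Disease (SD". Section 6.3 has the same, "Clinical Benefit Rate (CBR, defined as CR + PR + Stable Disease (SD", and section 10.1.2 repeats it. None of the three adds a time requirement.

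SD is defined once, in section 6.6.1, on the summed diameters of target lesions: "Neither sufficient shrinkage to qualify for PR nor sufficient increase to qualify for PD, taking as reference the smallest sum diameters while on study". For non-target disease, section 6.6.2 offers CR, PD and one category between them: "Non-CR/Non-PD: Persistence of one or more non-target lesion(s) and/or maintenance of tumor marker level above the normal limits". Section 6.6.4 says how long SD lasts ("Stable disease is measured from the start of the treatment until the criteria for progression are met") but sets no threshold.

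On who is counted:

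- Section 3.1.4 admits patients with or without measurable disease, and section 6.2 says that IBC patients often lack it.
- Section 6.2 also lets response be called in non-measurable-only disease by comparison with the change required in measurable disease, and defines CR there as disappearance.
- Section 6.4 restricts evaluability for objective response to patients with measurable disease and gives non-target disease a separate category.
- Section 6.7 makes everyone with one on-study scan evaluable for ORR and CBR.

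Sections 2.2.1, 5.0 and 6.1 schedule response scans every 12 weeks (±1 week in 6.1). Section 6.2 says every 8 weeks.

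**The concern.** Two patients show the problem. One has a measurable lesion, is stable at the week-12 scan and progresses soon after. The other has bone-only or skin-only disease that persists without progressing for a year. On the literal text the first is a clinical benefit. The second is Non-CR/Non-PD, which is not in the formula, although section 6.7 still puts her in the denominator.

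SD is also the component with the lightest requirement. Section 6.1 asks for a confirmatory scan only when the response is better than SD, so SD needs neither confirmation nor duration.

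What is at stake is the reading of a named secondary endpoint. In an open-label, single-arm trial, the reported rate would depend on the mix of measurable and non-measurable disease and on a coding decision that could be made after the data are seen.

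**Working it through.** **Inputs.** Section 10.2: "We will test the null hypothesis that median PFS is at most 3 months versus the alternative that it is at least 6 months", with exponential PFS, 15 then 29 patients, continuation if at least 8/15 are progression-free at 3 months, and rejection if at least 11/29 are progression-free at 6 months. First scan at 12 weeks (sections 2.2.1, 5.0, 6.1). The documents give no expected CBR and no figure for the share with only non-measurable disease.

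**1. The plan's own figures.** With p(t) = 0.5^(t/median), p(3) and p(6) are 0.50 and 0.25 under the null, and 0.7071 and 0.50 under the alternative. Let X ~ Bin(15, p(3)), continuing if X ≥ 8; Y given X ~ Bin(X, p(6)/p(3)); W ~ Bin(14, p(6)); reject if Y + W ≥ 11.

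- Null: early stop 50.0%, type I error 7.01%.
- Alternative: early stop 4.37%, power 90.1%.

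These match the stated 50%, 7%, 4.4% and 90%, so the same model can be used for CBR.

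**2. CBR if Non-CR/Non-PD is treated as SD.** Anyone without progression at the first scan is then CR, PR, SD or Non-CR/Non-PD, and counts. Twelve weeks is 84/30.4375 = 2.76 months.

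- Null: 0.5^(2.76/3) = 52.9%. Over the ±1 week window this is 55.7% (week 11) to 50.1% (week 13).
- Alternative: 0.5^(2.76/6) = 72.7%.
- If the 8-week interval in section 6.2 applied, the null figure would be 65.4%.

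**3. CBR if Non-CR/Non-PD is excluded and section 6.7 sets the denominator.** Let f be the share with only non-measurable disease. Assume the same PFS in both groups and ignore CRs and by-analogy responses in the non-measurable group. CBR is then the step 2 figure × (1 − f).

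| Assumed f | Null | Alternative |
|---|---|---|
| 0 | 52.9% | 72.7% |
| 0.2 | 42.3% | 58.2% |
| 0.4 | 31.7% | 43.6% |
| 0.6 | 21.1% | 29.1% |

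Once f exceeds 1 − 0.529/0.727 = 0.27, a regimen at the alternative coded this way has a lower expected CBR than a regimen at the null coded as in step 2.

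**4. CBR if section 6.4 sets the denominator.** Non-measurable-only patients drop out. On the same equal-PFS assumption the rates return to 52.9% and 72.7%, but in 29 × (1 − f) patients.

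**5. Effect of a minimum duration.** Taking 24 weeks (168/30.4375 = 5.52 months) as an illustration and counting Non-CR/Non-PD:

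- Null: 0.5^(5.52/3) = 27.9%.
- Alternative: 0.5^(5.52/6) = 52.9%.

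These are proportions still progression-free at 24 weeks. A confirmed responder who progressed before then would add to them.

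**The case against.** CBR is a secondary, descriptive endpoint with no hypothesis or decision rule attached. Section 10.3 plans Kaplan-Meier curves for PFS, so a reader can find the progression-free proportion at any time. The 12-week schedule already puts a practical floor of about 11 weeks under SD. Section 1.1.3 describes a cited clinical benefit rate as partial response plus disease stabilization with no duration, so the definition fits the protocol's own usage. A 24-week rule appears nowhere in the documents and nearly duplicates the 6-month PFS rate. Its gain in contrast is also modest: about 25 percentage points between null and alternative instead of 20, or odds ratios of about 2.9 instead of 2.4.

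Most of this stands. It limits the consequence and makes the choice of duration the sponsor's. It does not supply the missing category rule or settle the denominator.

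A reader might infer that lasting control of non-measurable disease can never count. The documents do not support that: CR counts, section 6.2 allows response by analogy, and nothing forbids coding Non-CR/Non-PD as SD. The rule is unstated. A reader might also infer that an inactive regimen would show 53% in the whole cohort while non-measurable-only patients are shut out. Both cannot hold at once, because 53% requires those patients to count, or to be outside the denominator.

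**Conclusion.** The definition is deficient in three linked ways: no minimum duration, no place for Non-CR/Non-PD, and a denominator on which sections 6.4 and 6.7 disagree. With the true PFS distribution held at the null, the expected CBR runs from about 53% down to 21% depending on how Non-CR/Non-PD is coded and on f.

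The 53% rests on exponential PFS with a 3-month median and a scan at exactly 12 weeks. It describes a regimen at the historical-control null, which need not mean no activity at all. The values 0.2 to 0.6 for f are assumed, since section 6.2 says only that such patients are frequent. Section 6.7 also drops patients with no on-study scan. If a share e is lost that way and none of them was controlled, 52.9% becomes 52.9%/(1 − e), or 56%, 59% and 66% for assumed e of 0.05, 0.10 and 0.20.

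It would go too far to say that CBR cannot separate activity from natural course, since 53% against 73% is a real difference. The sample size, power, type I error and stopping rule of the primary test are unaffected.

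**What to change.** - In sections 2.2.1, 6.3 and 10.1.2, add Non-CR/Non-PD to the CBR formula alongside SD.
- Reconcile section 6.4 with section 6.7 so that ORR and CBR have one stated denominator. Changing the formula alone would leave this conflict in place.
- State a minimum duration for SD and Non-CR/Non-PD. The Cycle 3 Day 1 scan (24 weeks), already scheduled, is one option, not a requirement found in the documents.
- Report non-progression at the Cycle 2 Day 1 scan separately, labelled as 12-week disease control.
- Reconcile the 8-week interval in section 6.2 with the 12-week interval elsewhere, since the 12-week figure depends on it.

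The cost is wording; no scan, visit or patient is added. With a minimum duration the reported CBR will usually be lower, and a 24-week version will overlap with the 6-month PFS rate.
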